Sample Size	
A sample size of approximately 240 completed subjects (120 per arm) is estimated to provide approximately 80% power (at a 2-sided, 5% significance level) to detect a 0.8-point difference in WOMAC Pain subscale score (on a 0-10 scale) between EP-104IAR and vehicle (assuming a standard deviation of 2.2).
 
Assuming a 20% drop-out rate over the course of the study, approximately 300 subjects will be randomized and dosed.
 
Imaging Sub-Study
 
As this is an exploratory data collection, no power calculations have been considered.

Statistical Methods	
Efficacy Analyses
 
The primary efficacy endpoint is the difference in change from baseline between EP-104IAR and vehicle in WOMAC Pain at Week 12. The primary analysis will be performed in the ITT population.
 
Change from individual pre-dose baseline WOMAC Pain will be fit to a mixed-effects for repeated measures model using all available data from the ITT population. This model will contain fixed effects terms for site; individual baseline WOMAC Pain; and the treatment-by-week interaction, where treatment and week are both treated as categorical variables; and a random per-patient intercept. An unstructured residual covariance matrix at the patient level will initially be fit; if this model fails to numerically converge, a compound symmetry structure will be used. No missing data imputation will be included in this model. Inferential results will be produced for the difference between EP-104IAR and vehicle at Week 12.
 
Key secondary endpoints will be analyzed using analogous methods. A step-down hierarchical testing procedure will be used, at the 5% level, where each endpoint may only be formally assessed inferentially if all prior endpoints were statistically significant at the 5% level.
 
Additional secondary and exploratory analyses, and covariate analyses, will also be conducted where appropriate (see Section 11.7.3).
 
Safety and Pharmacodynamic Analyses
 
 • Safety data (safety labs, cortisol, physical exams, knee exams, vital signs, etc.) will be summarized by treatment using standard summary statistics for both raw data and change from baseline. • Treatment-emergent adverse events (TEAEs) will be summarized by treatment.

- Impact on hypothalamic-pituitary-adrenal axis (ACTH stimulation test results) will be summarized by treatment using standard summary statistics.

Pharmacokinetic Analyses

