11.7 Efficacy Evaluations

11.7.1 Primary

The primary efficacy endpoint is the difference in change from baseline between EP-104IAR and vehicle in WOMAC Pain at Week 12, in the ITT population.

Baseline WOMAC Pain will be calculated at the individual level and is defined as the average of three measurements; 2 measurements during the Washout and Baseline Period and 1 at Visit 2 (pre-dose). Change from individual pre-dose baseline will then be calculated for each post-dosing weekly assessment from Week 1 through Week 24. A mixed-effects model for repeated measures (MMRM) model will then be fit to the change from baseline data for all subjects in the ITT population, including fixed effects terms for:

site (potentially grouped, a classification that will be made as part of the blind review process and documented in the SAP prior to formal study unblinding); individual baseline WOMAC Pain; and the treatment-by-week interaction, where treatment and week are both defined as categorical variables. A random per-patient intercept will also be included. An unstructured covariance matrix at the patient level will initially be fit; if this model fails to converge numerically, a compound symmetry structure will be used.

No imputation of missing data will be performed for this analysis; the MMRM model allows handling of missing data under a suitable set of missing data assumptions. If blinded data review indicates that those assumptions appear not to be met, or there is a non-negligible degree of missingness, suitable alternative modeling approaches will be detailed in the SAP prior to formal study unblinding.

In addition, if the PPS population markedly differs from the ITT population, identical analyses for the PPS population will be performed.

Inferential results will be presented comparing EP-104IAR versus vehicle.

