### 3. STATISTICAL METHODOLOGY

#### 3.1 General Principles

All collected study data will be presented in listings. All derivations and statistical analyses will be performed using SAS® software Version 9.4 (or higher) or Phoenix® WinNonlin® Version 8.3 (or higher) (Certara USA, Inc., Princeton, NJ). Prior and concomitant medications/procedures will be coded using World Health Organization (WHO) Drug Dictionary Enhanced March 1, 2021 (or most recent version prior to data base lock). Adverse events will be coded using Medical Dictionary for Regulatory Activities (MedDRA) Version 24.0 (or most recent version prior to data base lock).

Unless stated otherwise, descriptive summaries for continuous variables will include n (number of subjects with non-missing results), mean, standard deviation (SD), median,  $Q_1$ ,  $Q_3$ , minimum, and maximum. For categorical variables, n and percent will be provided. Percentages will be calculated out of the number of subjects in the given sample with a non-missing result.

The primary means of efficacy data collection will be via an electronic patient-reported outcome (ePRO) device. Subjects will be provided with a hand-held device programmed to prompt the subject to record data as required throughout the study. The primary means of non-efficacy data collection will be via the electronic case report forms (eCRFs).

Summaries presented by collection day and/or by time point will be based on scheduled assessments as planned in the protocol except for all WOMAC data (See Section 4.1). Unscheduled assessments will be presented in listings and will not be included in the analyses except for: determination of baseline as described in Section 4.3, ACTH stimulation test summaries (See Section 4.4), and for the derivation of PK parameters.

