### 3.7 Primary Endpoint Analysis

The primary efficacy endpoint is the difference in change from baseline between EP-104IAR and vehicle in WOMAC Pain at Week 12, in the ITT population. Baseline WOMAC Pain will be calculated at the individual level and is defined as the average of no more than three pre-dose measurements including the three scheduled measurements: 2 measurements during the Washout and Baseline Period and 1 at Visit 2 (pre-dose). If the subject has less than three pre-dose measurements, the average of all available pre-dose measurements will serve as the subject's baseline value. If a subject has more than three pre-dose measurements, then the three measurements collected immediately prior to pre-dose will be used to derive baseline WOMAC pain and earlier measurements will not contribute.

Change from individual pre-dose baseline will then be calculated for each post-dosing weekly assessment from Week 1 through Week 24. A mixed-effects model for repeated measures (MMRM) model will then be fit to the change from baseline data for all subjects in the ITT population, including fixed effects terms for: site (potentially grouped, see Section 4.2 for more details); individual baseline WOMAC Pain; and the treatment-by-week interaction, where treatment and week are both defined as categorical variables. A random per-patient intercept will also be included. An unstructured covariance matrix at the patient level will initially be fit; if this model fails to converge numerically, a compound symmetry structure will be used.

No imputation of missing data will be performed for this analysis; the MMRM model allows handling of missing data under the assumption that data is missing at random (MAR). To assess robustness to the assumption that data is missing at random, a multiple imputation approach will be used. Under this approach, outcome data will be imputed according to the following logic:

	EP-104IAR-201 Statistical Analysis Plan	Version: Final 1.0
	Date: 14-Jun-2023	Page 18 of 38

- If missing data is due to lack of efficacy (as captured by the Study Termination page on eCRF), data will be imputed as if subjects received placebo.
- If missing data is due to other reasons, data will be imputed as if subjects received their actual treatment.

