The imputation procedure will begin by generating 100 imputed datasets with SEED=1867004294, excluding subjects that discontinued due to lack of efficacy. The 100 imputed datasets for the WOMAC Pain scores will be generated separately for each randomized treatment with a fully conditional specification (FCS) model using the regression method. Following these initial imputations, 100 copies of the non-missing WOMAC Pain scores for subjects that discontinued due to lack of efficacy will be generated. One of these copies will be added to each of the 100 imputed datasets generated for the placebo group. A single imputation will then be generated for each of these 100 combined sets of data using the same FCS model as above. This will result in 100 imputed datasets for all subjects.

Change from baseline to Week 12 in WOMAC Pain from each of the 100 imputed datasets will be analyzed separately using an ANCOVA model with effects treatment, site (possibly grouped; see Section 4.2) and baseline WOMAC Pain. For each comparison of interest, estimates and their associated standard errors from the ANCOVA models will be combined to produce a single overall estimate and standard error. Associated confidence intervals and p-values will then be generated as appropriate.

The SAS® MI procedure will be utilized for imputing data. The first imputation step is described above.

The imputation step for subjects randomized to EP-104IAR that discontinued due to lack of efficacy will be similar to the step above except with SEED=454120304, NIMPUTE=1, and without “by trt” since imputation will be based on a single treatment group.

The results of the 100 analyses will be transformed into a normal statistic and combined into a single analysis using PROC MIANALYZE.

In addition to the robustness analysis described above, if the PPS population markedly differs from the ITT population, identical analyses for the PPS population will be performed. Subject to finalization after the blind review, the PPS population will be considered significantly different if it is less than 85% of the ITT population.

	EP-104IAR-201 Statistical Analysis Plan	Version: Final 1.0
	Date: 14-Jun-2023	Page 19 of 38

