## 3.8 Secondary Endpoint Analyses

### 3.8.1 Key Secondary Efficacy Endpoints

The following secondary endpoints will be assessed in a hierarchical manner, comparing EP-104IAR versus vehicle. If the primary endpoint is statistically significant at the 5% level, then the first secondary endpoint may be formally assessed for statistical significance. If the first secondary endpoint is statistically significant at the 5% level, then the second secondary endpoint may be formally tested, and so forth. Upon failure of any inferential test at the 5% level, no subsequent secondary endpoints may be declared to be statistically significant. Analysis of these secondary endpoints will be based on the ITT population. If the PPS population markedly differs from the ITT population as described above, identical analyses for the PPS population will be performed.

The endpoints are as follows:

- Difference in change from baseline between EP-104IAR and vehicle in WOMAC Function at Week 12
  - Analysis will be identical to that described for the primary endpoint.
- Difference between EP-104IAR and vehicle in the area under the WOMAC Pain-time curve to 12 weeks post-dose
  - Area under the curve in change from baseline WOMAC Pain from Week 0 to Week 12 will be calculated on a per-individual basis using the linear trapezoidal rule. AUC will be normalized to account for subjects whose actual days and nominal days at Week 12 differ. Treatments will be compared using an ANCOVA model containing site (possibly grouped, see Section 4.2); individual baseline WOMAC Pain; and treatment group as covariates.
- Difference in change from baseline between EP-104IAR and vehicle in WOMAC Pain at Week 24
  - Analysis will be identical to that described for the primary endpoint.
- Difference between EP-104IAR and vehicle in Outcome Measures in Rheumatology-Osteoarthritis Research Society International (OMERACT-OARSI) strict responders at Week 12
  - The proportion of patients meeting the strict responder definition at Week 12 will be compared (EP-104IAR versus placebo) using Fisher's exact test. Patients who discontinue prior to Week 12 will be considered non-responders.
  - Strict responders, under the OMERACT-OARSI criteria, are defined as  $\geq 50\%$  improvement in WOMAC Pain or Function score and an absolute change  $\geq 2$  in the respective score (scores scaled 0 – 10).

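### The primary MMRM's random patient intercept duplicates what its unstructured covariance already holds, and the compound-symmetry fallback can misstate the standard error for Pain at Week 24

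*SAP*

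**What the plan says.** The primary analysis fits one model to the weekly changes from baseline in WOMAC Pain from Week 1 to Week 24. SAP 3.7 says of the covariance: "A random per-patient intercept will also be included. An unstructured covariance matrix at the patient level will initially be fit". Protocol 11.7.1 has the same pairing and gives the fallback: "if this model fails to converge numerically, a compound symmetry structure will be used". The Statistical Methods part of the protocol synopsis settles where the matrix sits: "An unstructured residual covariance matrix at the patient level will initially be fit". It is a residual matrix, in the model together with the random intercept.

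SAP 3.1 names the software ("All derivations and statistical analyses will be performed using SAS"). No procedure, option, standard-error type or degrees-of-freedom method is given for the MMRM, whereas SAP 3.7 does name procedures for the multiple imputation. Non-convergence is not defined.

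SAP 3.8.1 lists as the third key secondary endpoint "Difference in change from baseline between EP-104IAR and vehicle in WOMAC Pain at Week 24", with the instruction "Analysis will be identical to that described for the primary endpoint". Protocol 11.7.2 confirms that the Week 24 estimate is taken from the same analysis.

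**The concern.** There are two linked problems.

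First, a random intercept adds one constant to every element of the patient-level covariance matrix. An unstructured matrix can absorb that constant, so the likelihood is flat in one direction. Depending on how the software treats the singularity, this could be read as a convergence failure and trigger the fallback.

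Second, the fallback goes straight from 300 covariance parameters to homogeneous compound symmetry, which assumes the same variance at every week and the same correlation at every lag. The documents give a single SD of 2.2 and nothing to support constant variance for 24 weeks after one injection. A pooled variance is usually close to right in the middle of the series and worst at its ends. Week 24 is the last week, and its test is alpha-controlled.

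**Working it through.** **The plan's own figure.** SAP 3.3 gives a two-sided 5% level, 80% power, a difference of 0.8 and an SD of 2.2. Then n = 2 × (1.960 + 0.842)² × 2.2² / 0.8² = 118.7, or 119 per arm, against the plan's 120. Power at 120 is 80.4% (80.1% by the noncentral t). With 20% drop-out, 120 / 0.8 = 150 per arm. The sample size is not in question.

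**Redundancy.** The marginal covariance is V = σ²J + R, with J a matrix of ones and R unstructured. Over 24 weeks R has 24 × 25 / 2 = 300 free elements. With σ² there are 301 parameters, and the map to V has rank 300. Under compound symmetry plus intercept there are 3 parameters and rank 2, so the fallback has the same fault. V is unchanged either way, so no treatment estimate or standard error changes.

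**Fallback, hand check without drop-out.** Assume the SD rises linearly from 1.83 at Week 1 to 2.60 at Week 24 and is 2.2 at Week 12, with 150 per arm. The variance averaged over the 24 weeks is 4.97.

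- Model SE at Week 24: √(2 × 4.97 / 150) = 0.257
- True SE at Week 24: √(2 × 2.60² / 150) = 0.300
- Ratio 0.857, so type I error = 2 × [1 − Φ(1.96 × 0.857)] = 9.3%

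Reversing the profile gives a ratio of 1.216 and 1.7%.

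**Fallback with 20% drop-out, independent of outcome.** The compound-symmetry parameters are those that maximise the expected likelihood under the assumed true covariance. Type I error is 2 × [1 − Φ(1.96 × SE_model / SE_true)]. The true correlation is assumed to be 0.45 + 0.55 × 0.9^lag, and SD is 2.2 at Week 12. For a 30% rise, SE_model is 0.264 and SE_true is 0.310. The ratio is 0.852, giving 9.5%. The simulation used 150 per arm and 2,000 runs per profile (Monte Carlo SE 0.4 to 0.7 points).

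| SD profile, Week 1 to 24 | Week 24, large sample | Week 24, simulated |
|---|---|---|
| Constant | 5.9% | 6.0% |
| Rises 20% | 8.4% | 8.8% |
| Rises 30% | 9.5% | 9.4% |
| Rises 50% | 11.6% | 10.8% |
| Falls 20% | 3.4% | 3.5% |
| Falls 30% | 2.2% | not run |
| 1.6 rising to 2.2 at Week 12, then flat | 7.9% | 9.0% |

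At Week 12 the large-sample values are 4.8% to 5.1% for the linear profiles and 7.1% for the plateau (simulated 4.7% to 5.9%, and 8.1%).

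**Other correlations** (exchangeable 0.6, 0.9^lag, 0.95^lag), Week 24: 5.0% to 6.4% at constant SD, 7.4% to 8.8% for a 20% rise, 10.6% to 12.0% for a 50% rise and 2.6% to 3.9% for a 20% fall. With exchangeable correlation and constant SD the fallback is exact (5.0%).

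**Remedy tested on the same simulated fits.** Sandwich standard errors with t on 298 degrees of freedom gave 4.4% to 5.9% at Week 24 and 4.7% to 6.0% at Week 12.

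**Convergence.** The unstructured matrix alone converged in 120 of 120 simulated data sets, in at most 14 iterations. The unstructured-plus-intercept fit was not run. None of this used SAS, and site and baseline terms were omitted.

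**The case against.** The redundancy has no demonstrated consequence: it alters no result, and whether it would trigger the fallback was not tested. The standard-error problem needs two further things, that the fallback is used and that the variance drifts. The documents inform neither, and the direction of error is unknown. All of this stands and limits the weight of the point.

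The hierarchy also matters. Pain at Week 24 is tested only after Pain at Week 12, Function at Week 12 and the Pain AUC have succeeded. Assume a Function–Pain correlation of 0.75, an equal standardised effect on Function, a constant 0.8-point effect to Week 12 and none at Week 24, with 120 per arm. The earlier tests then pass about 71% of the time, and a false Week 24 claim occurs in 5.0%, 5.7% and 7.1% of trials for SD rises of 20%, 30% and 50%. Under a global null it is at most 0.3%. But the hierarchy only lowers the chance of reaching the test; it does not correct its standard error. With a 1.2-point effect at Week 12 the figures are 7.8%, 8.8% and 10.8%.

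There are also cross-checks. The imputation analysis uses Week 12 variance only: "Change from baseline to Week 12 in WOMAC Pain from each of the 100 imputed datasets will be analyzed separately using an ANCOVA model". The instruction that Week 24 be analysed like the primary, the phrase "For each comparison of interest, estimates and their associated standard errors from the ANCOVA models will be combined" and the cross-reference in SAP 4.3 could extend it to Week 24, but this is not stated. The subgroup ANCOVAs in SAP 3.8.3 include Week 24 and the weekly SDs will be reported. These could expose a wrong standard error; they do not replace the formal test.

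Finally, heterogeneous compound symmetry with its model standard error also does well (5.7% at Week 12 and 4.6% at Week 24 in every SD profile). It was checked at one correlation only, and it still assumes equal correlation at every lag.

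**Conclusion.** The concern holds and is minor. The redundancy is a matter of algebra and is harmless to the estimates if the fit succeeds. The fallback rule is the substantive part: if it is invoked and variance changes over follow-up, the model-based standard error at Week 24 is wrong. A 20% to 50% rise in SD puts the nominal 5% test at roughly 7% to 12% across the correlations tried, and a 20% fall puts it at about 3% to 4%. The Week 12 primary is little affected under linear drift, but reaches 7.1% if the SD climbs from 1.6 and levels off at Week 12. These figures illustrate assumed covariances and drop-out independent of outcome; they are not established properties of this trial. The probability that the fallback is used has not been shown and may be low.

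**What to change.** Before unblinding, amend SAP 3.7 and record the change in SAP Section 5 as a departure from Protocol 11.7.1:

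1. Delete the random patient intercept and fit the unstructured residual covariance alone.
2. State that any structured fallback will be reported with empirical (sandwich) standard errors and a named degrees-of-freedom rule, for example t with the number of analysed subjects minus the rank of the between-subject fixed effects.

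Useful additions would be to define failure to converge, to try heterogeneous compound symmetry before the homogeneous form, to name a small-sample method such as Kenward-Roger for the unstructured fit (not tested here), and to state whether the imputation analysis also covers Week 24.

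The cost is one deleted sentence, one added sentence and a little code. Sample size and endpoints do not change. Sandwich standard errors are slightly less stable (simulated error 4.4% to 6.0% with 150 per arm), and they do not remove bias if drop-out depends on outcome and the covariance is misspecified.

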### 3.4 Analysis Populations

Evaluation of the primary and secondary efficacy endpoints will be performed using the Intention-to-Treat (ITT) Population. In addition, if the Per-protocol Set (PPS) Population markedly differs from the ITT population, as discussed in Section 3.7, identical analyses for the PPS population will be performed for the primary and key secondary endpoints. Safety endpoints will be analyzed using the Safety Population. Pharmacokinetic (PK) data will be analyzed using the Safety Population.

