#### 3.4.1 Intention-to-Treat Population

The intention-to-treat (ITT) population consists of all subjects who are both randomized to and receive treatment. Analysis will be conducted allocating subjects to the treatment to which they were randomized, irrespective of what was actually received.

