#### 3.4.2 Per-protocol Set Population

The per-protocol analysis set (PPS) population consists of all randomized subjects who received a dose of randomized treatment, had at least 1 post-baseline assessment, and had no major protocol violations potentially impactful of efficacy data. The subjects in this group will be analyzed based on the treatment they received.

	EP-104IAR-201 Statistical Analysis Plan	Version: Final 1.0
	Date: 14-Jun-2023	Page 16 of 38

Major protocol violations leading to exclusion from the per-protocol set population will be finalized after the blind review process and will be documented in a memo prior to unblinding of treatment assignments and database lock. All protocol deviations will be listed by subject.

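### The supportive per-protocol analysis hangs on a provisional cut on pooled set size, so it can be skipped even when 30% of one arm has been excluded

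*SAP*

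**What the plan says.** Protocol 11.7.1 makes the per-protocol analysis conditional without giving a number: "if the PPS population markedly differs from the ITT population, identical analyses for the PPS population will be performed". SAP 3.7 supplies the number: "the PPS population will be considered significantly different if it is less than 85% of the ITT population". The same sentence opens with a qualifier, "Subject to finalization after the blind review", so the 85% is a working value.

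The condition reaches beyond the primary endpoint. SAP 3.4 says that when it is met "identical analyses for the PPS population will be performed for the primary and key secondary endpoints", and SAP 3.8.1 refers back to it: "If the PPS population markedly differs from the ITT population as described above".

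Both sets in the ratio are defined over all subjects. The ITT set "consists of all subjects who are both randomized to and receive treatment" (SAP 3.4.1). To be in the PPS, a subject must have been dosed, have a post-baseline assessment and have "had no major protocol violations potentially impactful of efficacy data" (SAP 3.4.2). The violations that lead to exclusion are settled after the blind review and "will be documented in a memo prior to unblinding of treatment assignments".

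Two other provisions matter. SAP 3.5 reports the number of subjects in each analysis set by treatment arm, whether or not the trigger fires. Protocol 8.1 keeps subjects who take a prohibited or restricted therapy after dosing in the study, warns that some analyses may leave out their data, and defers the details to the SAP.

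**The concern.** The written trigger has a single input, the pooled PPS count divided by the pooled ITT count. Nothing in either document makes the decision depend on which arm the exclusions come from or why they were made.

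Unequal exclusion is plausible here. Protocol 8.1.3 prohibits oral NSAIDs, opioids and injected corticosteroids. If the product works, vehicle subjects have more reason to take them, and such use bears directly on Week 12 WOMAC Pain. This is a possible mechanism only. The documents give no expected violation rate, and the list of major violations is still to be fixed.

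The PPS analysis is the only planned efficacy analysis that takes major violators out. If the trigger stays silent, the report has no per-protocol estimate for the primary endpoint or for any of the four key secondary endpoints. The imbalance would become visible only after unblinding, when a per-protocol analysis can no longer be presented as pre-specified.

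**Working it through.** **Inputs.** From SAP 3.3: two-sided 5% level, 80% power, SD 2.2, difference 0.8, about 120 per arm, 20% drop-out, 150 per arm randomized and dosed. From SAP 3.2: 1:1 allocation. From SAP 3.7: the 85% cut, a strict less-than.

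**1. The plan's own figures.** Per arm, n = 2 × (1.960 + 0.842)² × 2.2² / 0.8² = 118.7, so 119. The plan says about 120, which gives 80.4% power by the normal formula and 80.1% by the noncentral t. Allowing for drop-out, 120 / (1 − 0.20) = 150. The sample size reproduces and is not in question. The planned ITT set is 150 + 150 = 300.

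**2. Where the trigger sits.** It fires if PPS/ITT < 0.85, and 0.85 × 300 = 255.
- 45 excluded: 255/300 = 85.0%, not below the cut, so it does not fire.
- 46 excluded: 254/300 = 84.7%, so it fires.

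**3. What 45 exclusions can look like.** These splits give the same pooled ratio and the same silent result:

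| Split of 45 | One arm | Other arm |
|---|---|---|
| 45 / 0 | 30.0% | 0.0% |
| 40 / 5 | 26.7% | 3.3% |
| 35 / 10 | 23.3% | 6.7% |
| 23 / 22 | 15.3% | 14.7% |

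The first row is the arithmetic limit of the rule. If the arms turn out slightly unequal, for example 148 and 152, the one-arm limit is 45/148 = 30.4% or 45/152 = 29.6%.

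**4. How often it would fire under unequal rates (assumed rates, not in the documents).** With binomial exclusions and 150 per arm, the rule fires when the total reaches 46. At 20% against 5%, the expected total is 30 + 7.5 = 37.5 and it fires in about 8% of trials. At 25% against 2%, the expected total is 37.5 + 3 = 40.5 and it fires in about 18%.

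**5. How far the two estimates could diverge (illustration only).** Take the limiting case. Let d be the gap in mean Week 12 change between the excluded 30% and the remaining 70% of that arm. The arm's ITT mean is 0.70 × (mean of remaining) + 0.30 × (mean of excluded), and its PPS mean is the mean of the remaining subjects. The other arm does not change, so PPS and ITT differ by 0.30 × d.
- d = 1: 0.30 points, and 0.30/0.8 = 37.5% of the design difference.
- d = 2.2: 0.66 points, and 0.66/0.8 = 82.5% of the design difference.

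This uses raw means with Week 12 scores for everyone; the planned model would move the figures somewhat. Both the split and d are assumptions. The value 2.2 is the planning SD of individual change, borrowed here as an upper value for a gap between subgroup means.

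**The case against.** The strongest reply is that nothing depends on the PPS. ITT is the analysis set for the primary and key secondary endpoints, and the testing hierarchy does not use the PPS. When exclusions are unbalanced and related to outcome, a PPS contrast loses the protection of randomization, so the estimate is hardest to interpret where it is most wanted. All of this stands, and it keeps the point small.

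Second, the 85% is provisional. The blind review could change it, and it can see pooled reasons and pooled pain scores. That is true, but it cannot see arms, and the SAP names no other criterion. Another pooled percentage would leave the same gap.

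Third, the plan already reports set sizes by treatment (SAP 3.5) and lists every deviation by subject (SAP 3.4.2). A split of 105/150 against 150/150 would therefore be visible. It would not prompt a per-protocol estimate. The multiple-imputation analysis in SAP 3.7 runs regardless, but it deals with missing data and leaves in violators who have observed scores.

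Four stronger readings are tempting, and the documents support none of them:
- That the rule exists to detect unbalanced or pain-related violations and fails at its job. No section states a purpose, and a size cut that avoids near-duplicate tables is an ordinary reading.
- That an untriggered rule would be offered as evidence that the estimates agree. The SAP does not say so.
- That firing on balanced exclusions, such as 23 + 23, is a fault. It costs only extra tables, which always running the analysis would also produce. Nor does balance guarantee equal estimates: the gap between excluded and retained subjects must also match across arms.
- That 0.30 to 0.66 points is bias in the trial result. It is the distance between PPS and ITT under assumed inputs.

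**Conclusion.** The point holds as a minor improvement to the plan. As written, a provisional cut on pooled size decides whether the only efficacy analysis without major violators is run. At the planned 300 subjects it stays silent for up to 45 exclusions however they split, the limit being 30% of one arm against none of the other. A blind review cannot correct for that.

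The 45-exclusion limit follows from SAP 3.3 and 3.7 alone. The firing rates and the 0.30 to 0.66 point divergence rest on assumed exclusion rates, splits and gaps for which the documents give no basis. No primary or key secondary conclusion, error rate or ITT estimate is affected, and any PPS contrast with unbalanced exclusions would need cautious interpretation.

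**What to change.** - Delete the 85% trigger in SAP 3.7 and the conditional wording in SAP 3.4, 3.7 and 3.8.1.
- Always run the PPS analysis of the primary and the four key secondary endpoints, labelled supportive.
- Add PPS exclusions by arm and reason to the disposition table in SAP 3.5, which already gives set sizes by arm.
- Record the departure from Protocol 11.7.1 in SAP section 5.

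Keep ITT primary and the testing hierarchy unchanged. The exclusion list should still be fixed before unblinding, as SAP 3.4.2 provides.

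Applying 85% within each arm would be a weaker remedy. It would catch 45 against 0, but it could not be evaluated at a blind review. It would also stay silent at 22 exclusions in one arm (128/150 = 85.3%) and none in the other.

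The cost is SAP wording and five supportive analyses from the same programs, with no new data. Some of the tables will nearly duplicate the ITT results.
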